6.2.3. Data derivation

6.2.3.1. Age at first dose in years

Age will be calculated as the number of years between the date of birth and the date of first vaccination.

In case of partial dates, the following 2 dates will be used as replacement dates:

- 15th of month, if the day is missing.
- 30th of June, if day and months are missing.

6.2.3.2. Age category at vaccination

As only the year of birth will be collected in the eCRF, there might be some discrepancies between the age computed using standard derivation rules and the age category used in SBIR for the minimization.

Therefore, for the analysis by age, the age categories will be determined according to the information entered in SBIR (add name of variable in SDTM), except for “ ≥ 65 YOA” category which will be obtained using the derived age because this category is not used in SBIR for minimization.

6.2.3.3. Temperature

Temperatures will be presented in degrees Celsius ($^{\circ}\text{C}$). Temperatures reported in degrees Fahrenheit ($^{\circ}\text{F}$) will be converted as follows:

$$\text{Temperature (Celsius)} = ([\text{Temperature (Fahrenheit)} - 32] \times 5)/9$$

[figure not shown]
6.2.3.4. Numerical serology results

Numerical serology results will be derived from the content of IS.ISORRES in the SDTM dataset. For all the assays available for the study, the following derivation rules apply:

IS.ISORRES	Derived value
“NEG”, “-”, or “(-)”	cut-off/2
“POS”, “+”, or “(+)”	cut-off
“< value” and value is \leq assay cut-off	cut-off/2
“< value” and value is $>$ assay cut-off	value
“> value” and value is $<$ assay cut-off	cut-off/2
“> value” and value is \geq assay cut-off	value
“value” and value is $<$ cut-off	cut-off/2
“value” and value is \geq cut-off	Value
“value” and value is $>$ ULOQ	ULOQ
All other cases	missing

Note: The Reverse Cumulative Distribution curves (RCC) generated will not use the ULOQ values but the exact value if the exact value is greater than ULOQ.

CCI

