Starting with an initial dilution of 1:10, a dilution series (by a factor of 2) is prepared up to an end dilution of 1:10 240. The titration endpoint is taken as the highest dilution step that shows complete inhibition of hemagglutination. All assays are performed in duplicate. The usual cut-off value is = 10 1/DIL.

10.3. Appendix 3: Adverse Events: definitions and procedures for recording, evaluating, follow-up, and reporting Definition of AE**10.3.1. Definition of an AE**

An AE is any untoward medical occurrence (an unfavorable/unintended sign – including an abnormal laboratory finding), symptom, or disease (new or exacerbated) in a clinical study participant that is temporally associated with the study intervention. The AE may or may not be considered related to the study intervention.

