4.1.2. Definitions

- For the RSV antigens:

A seronegative participant will be defined as a participant whose antibody titer/concentration is below the cut-off value of the assay. A seropositive participant is a participant whose antibody titer/concentration is greater than or equal to the cut-off value of the assay.

MGI (mean geometric increase): The geometric mean of the within participant ratios of the post-dose titer over the pre-dose titer.

- For the FLU antigens:

SCR (seroconversion rate): The percentage of vaccinees who have either a HI pre-dose titer $< 1:10$ and a post-dose titer $\geq 1:40$ or a pre-dose titer $\geq 1:10$ and at least a four-fold increase in post-dose titer.

HI SPR (seroprotection rate): The percentage of vaccinees with a serum HI titer $\geq 1:40$ that usually is accepted as indicating protection.

MGI (mean geometric increase): The geometric mean of the within participant ratios of the post-dose titer over the pre-dose titer.

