4.3.1.2. Within groups assessment

For each group, at each time point that blood samples are collected for humoral immune response and for each assay (unless otherwise specified):

- Percentage of participants above pre-defined assay cut-off and their exact 95% CI will be tabulated.
- Percentage of participants above seroprotection/seroconversion rate for HI antibody titer and their exact 95% CI will be tabulated.
- ~~CCI~~ /GMTs and their 95% CI will be tabulated.
- MGI will be tabulated with 95% CI.
- Antibody titer/concentration will be displayed using reverse cumulative curves.

The above mentioned descriptive within group immunogenicity analysis will also be generated by age at first vaccination (65-69 YOA, 70-79 YOA, ≥ 70 YOA and ≥ 80 YOA years).

- Additionally, the CBER and CHMP criteria for HI SPR and SCR will be assessed as follows:

CBER criteria to be evaluated:

- The lower limit (LL) of the 95% CI for SCR should be $\geq 30\%$ in participants ≥ 65 YOA.
- The LL of the 95% CI for SPR should be $\geq 60\%$ in participants ≥ 65 YOA.

CHMP criteria to be evaluated:

- At least one of the 3 following criteria should be met:
- the point estimates of SPR $> 60\%$, SCR $> 30\%$, and MGI > 2.0 for elderly > 60 years for each of the antigen strains.

These above defined analyses evaluating the CBER and CHMP criteria should be interpreted with caution considering that there is no adjustment for multiplicity for these comparisons.

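### SAP 6.2.3.4 stores a '< value' result above the cut-off at the bound itself, so an HI result of '<40' would be scored as 40: a minor, easily corrected rule, because such results should be rare

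*SAP*

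**What the plan says.** SAP 6.2.3.4 opens its derivation table with "For all the assays available for the study, the following derivation rules apply", so the HI titers are covered. Two rows deal with results reported only as lying below a bound:

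- "< value” and value is \leq assay cut-off": the derived number is half the cut-off.
- "< value” and value is $>$ assay cut-off": the derived number is the bound.

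Protocol section 10.2 (Appendix 2) gives the HI cut-off: "The usual cut-off value is = 10 1/DIL". It describes the titration this way: "Starting with an initial dilution of 1:10, a dilution series (by a factor of 2) is prepared".

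SAP 4.1.2 defines the seroprotection rate (SPR) as "The percentage of vaccinees with a serum HI titer $\geq 1:40$ that usually is accepted as indicating protection". It defines seroconversion (SCR) as either a pre-dose titer under 1:10 with a post-dose titer of at least 1:40, or a pre-dose titer of at least 1:10 with at least a four-fold rise.

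Neither document exempts SPR or SCR from the derived numbers, asks for a retest of such sera, or sets them to missing. The main-analysis text in SAP 4.2.2 covers only titers below the cut-off or above the upper limit of quantification.

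**The concern.** The bound is the one value that a '< value' result is known not to reach. Storing the bound is harmless for a threshold lying elsewhere. It is wrong when the bound coincides with a threshold that is itself counted as a success, and the HI threshold of 40 is of that kind. The derived number then contradicts the laboratory result.

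The derived numbers feed SPR and SCR, the 10-point SCR reference criterion (SAP 4.3.1.1) and the CBER and CHMP checks (SAP 4.3.1.2). They also feed the GMTs and mean geometric increases. A post-dose result stored too high inflates these. A pre-dose result stored too high lowers the fold rise and can hide a true seroconversion.

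**Working it through.** **Inputs.** HI cut-off 10 and two-fold steps from 1:10 (Protocol 10.2); SPR and SCR definitions (SAP 4.1.2); 462 evaluable per group, 10-point SCR margin and one-sided 2.5% (SAP section 5 and 4.3.1.1). The number of '<40' results is not in the documents, so the counts below are assumptions.

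**The plan's own figure.** SCR power with no true difference is Φ(0.10/SE − 1.96), with SE = √(2p(1−p)/462). For p = 0.50, SE = 0.0329, 0.10/SE = 3.04, and power is 86.0%. At 70, 50, 35 and 25% the formula gives 91.3, 86.0, 89.0 and 93.9%, against 91.3, 86.1, 89.0 and 93.9% in SAP Table 3. The sample size is not in question.

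**Post-dose results.** Each row applies the SAP rule, then value/2.

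| Pre-dose | Post-dose | Stored (SAP) | SPR / SCR (SAP) | Stored (value/2) | SPR / SCR (value/2) |
|---|---|---|---|---|---|
| '<10' (stored 5) | '<40' | 40 | yes / yes | 20 | no / no |
| 10 | '<40' | 40 | yes / yes (40/10 = 4) | 20 | no / no |
| 20 | '<40' | 40 | yes / no (40/20 = 2) | 20 | no / no |
| 40 | '<40' | 40 | yes / no | 20 | no / no |
| '<10' to 40 | '<20' | 20 | no / no | 10 | no / no |
| '<10' or 10 | '<80' | 80 | yes / yes | 40 | yes / yes |
| 20 | '<80' | 80 | yes / yes (80/20 = 4) | 40 | yes / no |

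A titer below 40 cannot meet either definition: SPR needs 40, SCR from under 10 needs 40, and a four-fold rise from 10 or more needs at least 40. So every SPR 'yes' in the '<40' rows is wrong, and so are the first two SCR entries. For '<80' the SPR status is unknown, since the titer may be 40 or lower. In the last row the SCR 'yes' is wrong as well, because a titer below 80 is not a four-fold rise from 20.

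**Pre-dose results.**
- '<40' is stored as 40, so SCR needs 4 × 40 = 160. On the two-fold series the true titer is at most 20, so a post-dose 80 is a seroconversion (80/20 = 4) that the rule scores as a failure (80/40 = 2). Value/2 scores it correctly.
- '<20' is stored as 20, so a post-dose 40 fails (40/20 = 2), although a true pre-dose titer of 5 or 10 would give seroconversion. Value/2 gives 40/10 = 4.

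**Size.**
- One post-dose '<40' moves SPR by 1/462 = 0.22 points; 5 move it by 1.1 and 10 by 2.2. SCR moves by the same amount for those falsely converted.
- The group GMT is inflated by (40/true titer)^(k/462). For true titers of 20 and 10, k = 5 gives 1.008 and 1.015; k = 10 gives 1.015 and 1.030.
- CBER limit for SPR, exact interval: 299/462 has a lower limit of 60.2% and 298/462 has 59.9%, so one serum matters only at that boundary.
- Worst case for the SCR criterion, assuming false conversions in 1% of Co-Ad (about 5 of 462) and none in Control: the one-sided error at a true 10-point deficit rises from 2.5% to 4.9% (Control rate 50%) or 5.2% (35%).

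**The case against.** The strongest objection is that the trigger is not in the documents. The HI series starts at the cut-off, so a serum with no inhibition reads '<10' and correctly becomes 5. A '<40' would need a higher first dilution or an incomplete series, and the documents neither describe nor exclude these. SAP 6.2 presents its rules as standard ones, so the presence of the row does not show that such results are expected. This stands, and it is the main reason the point is minor.

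A second objection is that the table also uses the bound in the other direction, for '> value' results at or above the cut-off, so the choice is only a convention. This stands in part. For GMTs, value/2 and the bound are both crude substitutions. For classification they differ: '>40' stored as 40 still falls correctly on the protected side, whereas '<40' stored as 40 crosses to the wrong one.

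A third objection is that the effect is not differential. The laboratory is blinded to assignment (Protocol 6.3.5), and HI samples are taken at Day 1 and Day 31 in both groups (Protocol Table 11). This stands: similar frequencies largely cancel in the SCR difference.

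A reader might infer three stronger things. The first is that any result below 1:40 is scored as seroprotected. It is not: '<10' becomes 5 and '<20' becomes 20. The second is that the SCR criterion loses control of its error. That needs the one-sided clustering assumed above, which nothing in the documents suggests. The third is that the primary GMT comparisons are compromised. The rule does enter those titers, but even ten such sera in one group shift its GMT by 1.5% to 3.0% for true titers of 20 to 10, against a ratio margin of 1.5.

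**Conclusion.** The rule is wrong for the inputs it addresses. Certain SPR misclassification is specific to a post-dose '<40'. SCR is misclassified when that result follows a pre-dose '<10' or 10, and more generally when the bound equals four times the pre-dose titer. Pre-dose '<40' and '<20' can hide true seroconversions.

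The practical effect is probably small. It is 0.22 points of SPR per serum at 462 per group, in secondary summaries that SAP 4.3.1.1 and 4.3.1.2 say to interpret with caution because there is no multiplicity adjustment. The judgement of small size rests on two things: the 1:10 starting dilution being used throughout, which makes such results rare, and blinded testing, which makes clustering by group unlikely. The counts of 5 and 10 sera are illustrations. No primary conclusion is shown to be at risk. Severity: minor.

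**What to change.** In SAP 6.2.3.4, change the row so that '< value' with value above the cut-off is stored as value/2 for all analyses. A '<40' then becomes 20, neither seroprotected nor seroconverted. On the HI two-fold series the smallest bound above the cut-off is 20, so halving never takes a result below 10.

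Do not set indeterminate results such as '<80' to missing. Dropping only results known to lie below a bound would be informative missingness and could push SPR upward. Instead, report the number of affected results per group. If there are any, add a sensitivity analysis that counts indeterminate post-dose results as non-responders.

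The cost is one table row, one programming rule and a count in the report. The sensitivity analysis is needed only if the count is not zero. Making the change before results are known avoids a post hoc judgement.

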6.2.3.6. Onset day

The onset day for an event (e.g. AE, concomitant medication/vaccination) is the number of days between the last study dose and the start date of the event. This is 1 for an event occurring on the same day as a study dose (and reported as starting after study dose).

6.2.3.7. Duration of events

For the duration of solicited AEs within the 4-day period:

- The duration of the event will be calculated as the sum of the individual days with the event reported as Grade 1 or higher or reported as missing during the solicited event period (see Section [6.2.2.3.1](#) for missing data). For Grade 3, the duration will be calculated as the sum of individual days with the event reported as Grade 3 or reported as missing during the solicited event period.

For the duration of solicited AEs ongoing beyond the 4-day period:

- The duration of the event will be calculated as the difference between the start (during the solicited period) and end date (if known) plus one day regardless of the intensity. For Grade 3, the entire duration of symptoms with a maximum intensity equal to Grade 3 will be considered.

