4.3.2. Safety analysis

The safety analysis will be performed on the ES as follows:

- The number and percentage of participants and doses with at least one administration site event AE (solicited and unsolicited), with at least one systemic AE (solicited and unsolicited) and with any AE during the 4-day (i.e. the day of vaccination and 3 subsequent days) and 30-day (i.e. the day of vaccination and 29 subsequent days) follow-up period will be tabulated with exact 95% confidence interval (CI) after each dose and overall. The same computations will be done for Grade 3 AEs, for Grade 3 non-serious AEs and for AEs resulting in a medically attended visit.

These analyses will present all solicited and unsolicited AEs, including SAEs and pIMDs (unless otherwise specified).

The above analysis will also be performed for the solicited symptoms only during the 4-day (i.e. the day of vaccination and 3 subsequent days) follow-up period.

- The number and percentage of participants reporting each individual solicited administration site AE (any grade, Grade 3 and resulting in medically attended visit) and solicited systemic AE (any grade, Grade 3 and resulting in medically attended visit) during the 4-day follow-up period (i.e. the day of vaccination and 3 subsequent days) will be tabulated for each group after each dose and overall. The percentage of doses followed by each individual solicited administration site AE (any grade, Grade 3 and resulting in medically attended visit) and solicited systemic AE (any grade, Grade 3 and resulting in medically attended visit) during the 4-day follow-up period (i.e. the day of vaccination and 3 subsequent days) will be tabulated, with exact 95% CI.
- For fever, the number and percentage of participants reporting fever by half degree (°C) cumulative increments during the 4-day follow-up period (i.e. the day of vaccination and 3 subsequent days) will be tabulated for each group after each dose and overall.
- The percentage of participants with each solicited administration site event and solicited systemic event (any grade and Grade 3) will be represented graphically for each group after each dose.
- The number of days with solicited events reported during the 4-day follow-up period will be tabulated for each individual solicited event using descriptive statistics (mean, minimum, Q1, median, Q3, maximum). The same computations will be done for Grade 3 solicited events.

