- The number and percentage of participants using concomitant medication (any medication and any antipyretic) during the 4-day and the 30-day follow-up period after each dose and overall will be tabulated with exact 95% CI.
- The number and percentage of participants using concomitant vaccination during the 30-day follow-up period after each dose and overall will be tabulated with exact 95% CI.
- Compliance in completing solicited events information will be tabulated after each dose and overall.

Some of the key safety analysis will be generated by age group at first vaccination (65-69 YOA, 70-79 YOA, \geq 70 YOA and \geq 80 YOA years) as mentioned below.

[figure not shown]
- The number and percentage of participants reporting each individual solicited administration site AE (any grade, Grade 3 and resulting in medically attended visit) and solicited systemic AE (any grade, Grade 3 and resulting in medically attended visit) during the 4-day follow-up period (i.e. the day of vaccination and 3 subsequent days) will be tabulated for each group after each dose and overall.

The number and percentage of participants with any unsolicited AEs during the 30-day follow-up period (i.e. the day of vaccination and 29 subsequent days) with its exact 95% CI will be tabulated by group and by MedDRA Primary SOC, HLT and PTs

- For clinicaltrials.gov and EudraCT posting purposes, percentage of participants of combined solicited and unsolicited non-serious adverse events during the 30-day follow-up period (i.e. the day of vaccination and 29 subsequent days) will be produced by System Organ Class and preferred terms and according to occurrence of each event.

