6.2.2.3. Daily recording of solicited events

6.2.2.3.1. *Studies with paper diaries*

For studies using paper diaries which have questions in the CRF indicating the presence or absence of solicited events, the following rules are applicable for all solicited events except fever:

- Denominators for the summary of administration site (or systemic) solicited events will be calculated using the number of participants who respond “Yes” or “No” to the question concerning the occurrence of administration site (or systemic) events.
- When a specific solicited event is marked as having not occurred following a specific study dose (i.e. SDTM CE.CEOCCUR=N for the specified post-dose period for the event in question), all daily measurements will be imputed as None.
- When a specific solicited event is marked as having occurred following a specific study dose (i.e. SDTM CE.CEOCCUR=Y for the specified post-dose period for the event in question), any missing daily recordings will be given imputed values to allow them to contribute to the ‘Any’ rows but not to specific grade rows of the solicited event summary tables.
- When the group of solicited events (administration site or systemic) occurred is missing (i.e. SDTM CE.CEOCCUR=""), all missing daily recordings will be considered as missing for the solicited event summary tables.

The following table shows how participants contribute to each category for a specific solicited event over the Day X to Day Y post-dose period:

Solicited event category	Participants included in the calculation of the numerator
Any	All participants with at least one occurrence of the adverse event at Grade 1, Grade 2, or Grade 3 between Day X and Day Y or with the adverse event marked as present and at least one missing daily recording between Day X and Day Y
At least Grade 1	All participants with at least one occurrence of the adverse event at Grade 1, Grade 2, or Grade 3 between Day X and Day Y
At least Grade 2	All participants with at least one occurrence of the adverse event at Grade 2 or Grade 3 between Day X and Day Y
At least Grade 3	All participants with at least one occurrence of the adverse event at Grade 3 between Day X and Day Y

For fever, the summary tables will not include the row ‘Any’. The missing daily records do not contribute to the number participants reporting fever by half degree (°C): >=38; >38.5, >39, >39.5 and >40.

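### Missing diary days are counted as Grade 3 days in the within-period duration summary, although the SAP's incidence rule leaves the same days ungraded

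*SAP*

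**What the plan says.** SAP Section 4.3.2 plans summary statistics (mean, minimum, quartiles, maximum) for the number of days with each solicited event in the 4-day follow-up, and adds: "The same computations will be done for Grade 3 solicited events".

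SAP Section 6.2.3.7 supplies the derivation. Any-grade duration is the "sum of the individual days with the event reported as Grade 1 or higher or reported as missing during the solicited event period", with a pointer to Section 6.2.2.3.1 for missing data. Grade 3 duration is the "sum of individual days with the event reported as Grade 3 or reported as missing during the solicited event period". For events that continue beyond the 4 days the rule is narrower: "For Grade 3, the entire duration of symptoms with a maximum intensity equal to Grade 3 will be considered".

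SAP Section 6.2.2.3.1 sets the missing-data rules for the incidence tables (fever is handled separately):

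- Event marked as not having occurred: "all daily measurements will be imputed as None".
- Event marked as having occurred: missing days count toward the 'Any' rows, "but not to specific grade rows of the solicited event summary tables".
- The numerator for at least Grade 3 is "All participants with at least one occurrence of the adverse event at Grade 3 between Day X and Day Y".

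**The concern.** The two sections give the same blank diary cell two meanings. For incidence it shows that the event was present at an unknown grade. For Grade 3 duration it is a severe day. Counting blanks in any-grade duration agrees with Section 6.2.2.3.1, because the event is known to have occurred. Counting them as Grade 3 does not, because nothing recorded supports that grade.

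The within-period Grade 3 rule also lacks the restriction that the beyond-period rule carries, and Section 4.3.2 does not define which participants have Grade 3 solicited events. Two programmers could therefore build different tables:

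- If anyone with a non-zero count enters, participants with only mild days and blanks appear in a Grade 3 table.
- If only participants with a recorded Grade 3 day enter, their blanks still lengthen the duration.

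Reactogenicity is a secondary objective, and this table describes how long severe reactions last. A reader would expect its number of participants to agree with the Grade 3 incidence row.

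**Working it through.** The documents state no Grade 3 duration and no diary missingness, so there is no figure of the plan's own to reproduce. The check applies both rules to every possible diary and then illustrates the effect on the mean under stated assumptions.

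**Step 1. Individual diaries (event marked as having occurred; M = missing)**

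| Days 1–4 | Grade 3 incidence (6.2.2.3.1) | Grade 3 days (6.2.3.7) | Recorded Grade 3 days |
|---|---|---|---|
| 1, 1, M, M | No | 2 | 0 |
| 1, M, M, M | No | 3 | 0 |
| 3, 1, M, M | Yes | 3 | 1 |
| 3, M, M, M | Yes | 4 | 1 |
| 3, 2, 1, 0 | Yes | 1 | 1 |

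**Step 2. All patterns.** Each day is Grade 0, 1, 2, 3 or missing, which gives 5⁴ = 625 patterns.

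- No recorded Grade 3 day: 4⁴ = 256 patterns, of which 3⁴ = 81 have no blank. The other 256 − 81 = 175 are credited with Grade 3 days: 108 with one, 54 with two, 12 with three and 1 with four.
- At least one recorded Grade 3 day: 625 − 256 = 369 patterns, of which 4⁴ − 3⁴ = 175 have no blank. The other 369 − 175 = 194 are lengthened: 148 by one day, 42 by two and 4 by three.

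These counts show which diaries the rule can affect. They are not expected frequencies.

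**Step 3. Effect on the mean (assumed inputs, not in the documents).** Of events marked as occurred, 5% have true grades 3, 3, 1, 0 and the rest 1, 1, 0, 0. Each day is missing independently with probability m, from 1% to 10%.

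- Recorded Grade 3 days only, among participants with at least one: 2(1 − m)/(1 − m²) = 2/(1 + m).
- SAP rule, same participants: Days 1 and 2 always count, whether recorded or blank, and Days 3 and 4 add 2m. The mean is 2 + 2m.
- SAP rule, anyone with a non-zero count: [0.05(2 + 2m) + 0.95 × 4m] / [0.05 + 0.95(1 − (1 − m)⁴)]. The denominator × 1000 is the number of participants in the table per 1000 events.

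| m | Recorded only | SAP rule, recorded Grade 3 required | SAP rule, any non-zero count | In table per 1000 events, any non-zero count |
|---|---|---|---|---|
| 1% | 1.98 | 2.02 | 0.139/0.0874 = 1.59 | 87 |
| 5% | 1.90 | 2.10 | 0.295/0.2262 = 1.30 | 226 |
| 10% | 1.82 | 2.20 | 0.490/0.3767 = 1.30 | 377 |

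About 50 per 1000 events have a recorded Grade 3 day. If the assumed Grade 3 share is varied from 2% to 10%, the mean for any non-zero count ranges from 1.18 to 1.76.

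**The case against.** There are four arguments on the other side.

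- **Incidence and duration are different statistics.** The rule in Section 6.2.2.3.1 governs rows of incidence tables, and its cross-reference sits in the any-grade sentence of Section 6.2.3.7, where the two rules agree. This is right as far as it goes: the conflict is between two treatments of the same missing cell, not two definitions of one statistic. But the SAP gives no reason for the difference and does not label the Grade 3 rule as a worst case.
- **Section 4.3.2 can be read as restricting the table.** Its reference to Grade 3 solicited events may mean participants who had one. On that reading the 175 blanks-only patterns and the enlarged table disappear. The SAP does not state it, and it would not stop blanks being added for those who remain: one Grade 3 day plus three blanks is still 4.
- **The effect may be small.** Protocol Section 10.3.7 has diary cards verified with the participant and unreturned ones sought. Blanks matter only for events marked as having occurred. Under the restricted reading and 1% missingness the illustrated mean moves only from 1.98 to 2.02. The SAP also plans that "Compliance in completing solicited events information will be tabulated after each dose and overall". This limits the size and shows how complete the data are, but does not correct the durations.
- **Fever is outside the general incidence rule.** True, but Section 6.2.2.3.1 also keeps missing temperature records out of the fever rows, so the mismatch remains.

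**Conclusion.** The concern holds on the SAP text. The within-period Grade 3 duration counts days with no recorded grade as severe, contrary to how the SAP grades the same days for incidence, and the population of the table is undefined. An individual duration can be overstated by up to 3 days when a Grade 3 day was recorded. It can be created entirely from blanks if the table is not restricted.

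The net effect on the tabulated mean cannot be given, because it depends on who enters the table and on a missingness rate that the documents do not report. In the illustration the mean rises by 0.04 to 0.38 days (2.02 − 1.98 and 2.20 − 1.82) if a recorded Grade 3 day is required. Otherwise it falls by 0.39 to 0.60 days (1.98 − 1.59 and, at 5% missingness, 1.90 − 1.30). These figures rest on the assumed profiles and on independent missingness.

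The scope is one descriptive safety summary. Grade 3 incidence, the primary non-inferiority tests, type I error and power are untouched. It should be corrected, but it does not threaten the trial's main conclusions.

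**What to change.** Amend SAP Section 6.2.3.7 so that within-period Grade 3 duration counts only days recorded as Grade 3. State in Section 4.3.2 that the Grade 3 duration table includes only participants with at least one recorded Grade 3 day. Keep missing days in the any-grade duration, where they agree with Section 6.2.2.3.1.

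The drawback is that a blank between two Grade 3 days is no longer counted, which can slightly understate duration. An optional sensitivity row that adds missing days for participants with a recorded Grade 3 day would show the upper bound.

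The cost is a few words in the SAP, one derivation line and, if wanted, one extra row. No new data are needed.
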